9.2 Sample Size

Sample size considerations were based on monitoring the primary efficacy endpoint, ORR, using a 2-arm Bayesian optimal phase 2 (BOP2) design (Zhao et al 2022).

Specifically, let n denote the interim sample size and N denote the maximum sample size. Let ORR_{con} denote the control ORR and ORR_{comb} denote the combination treatment ORR. We define the null hypothesis $H_0: ORR_{comb} \leq ORR_{con}$, under which the combination arm is deemed as unacceptable, respective to the control. We employ the following Bayesian rule to make a go/no-go decision:

(Futility stopping) stop enrolling patients and claim that the experimental arm is unacceptable if:

$$Pr(ORR_{comb} > ORR_{con} | data) < \lambda \left(\frac{n}{N}\right)^\alpha,$$

Where $\lambda=0.96$ and $\alpha=0.94$ are design parameters optimized to maximize the power under $H_0: ORR_{con} = 0.15$ and $ORR_{comb} = 0.43$, while controlling the type I error rate at 0.05 under $ORR_{con} = ORR_{comb} = 0.15$. This optimization is performed assuming a vague prior Beta(0.5,0.5) for ORR_{con} and ORR_{comb} .

An interim futility analysis is planned when ORR can be assessed for the first 39 patients, and the final ORR analysis is planned after 81 patients are followed for a minimum of 3 months (2 radiologic scans). A 2:1 combination:control randomization will be used for the 2 arms and will yield 83% power at the 1-sided 5% alpha based on the above decision rule to reject the null hypothesis and conclude that the combination arm is superior compared to the control:

At the interim analysis: $Pr(ORR_{comb} > ORR_{con} | data) > 0.5$, and

At the final analysis: $Pr(ORR_{comb} > ORR_{con} | data) > 0.96$

The go/no-go criteria, also presented in detail in Table 9 below, are non-binding.

The operating characteristics of the design, based on 100000 simulations using the BOP2 application, are presented in Table 10.

Table 9: Optimized Stopping Boundaries

Control N	Combination N	# CR/PR in Control	Stop for Futility if # of CR/PR in Combination - # of CR/PR in Control ≤
13	26	0	0
13	26	1~2	1
13	26	3	2
13	26	4	3
13	26	5	4
13	26	6	5
13	26	7	6
13	26	8	7
13	26	9	8
13	26	10	9
13	26	11	10
13	26	12	11
13	26	13	12
27	54	0	4
27	54	1	7
27	54	2	10
27	54	3	11
27	54	4	13
27	54	5	15
27	54	6	16
27	54	7	17
27	54	8	18
27	54	9	20
27	54	10	21
27	54	11	22
27	54	12~13	23
27	54	14	24
27	54	15	25
27	54	16~17	26
27	54	18~19	27
27	54	20~26	28
27	54	27	27

Abbreviations: CR = complete response; PR = partial response

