Table 10: Operating Characteristics

Scenario	% ORR Control	% ORR Combination	Early Futility Stopping (%)	Claim Promising (%)	Average Sample Size
1	15	15	46.1	4.6	62
2	23	23	43.8	4.5	63
3	20	40	7.1	54.6	78
4	23	43	7.7	52.9	78
5	25	50	4.5	68.6	79
6	15	43	1.9	82.7	80

Abbreviation: ORR = objective response rate

Additional futility monitoring criteria will be taken into consideration for the subgroup of patients with CPS ≥ 1 and < 20 . Specifically, if no more than one patient achieves a response (confirmed or unconfirmed CR or PR within the first two scans) in the first 10 patients enrolled in the combination arm for this subgroup, there will be no further enrollment in this subgroup, and the study will continue to enroll in the CPS ≥ 20 subgroup, consistent with any guidance based on the monitoring criteria outlined in [Table 9](#). Additionally, accrual in the CPS ≥ 1 and < 20 subgroup will pause, if no responses have been achieved, but response data for the first 10 patients in that subgroup are not yet mature, defined as at least 2 scans assessed.

Considering the limited size of the CPS ≥ 1 and < 20 subgroup, the futility criteria were derived based on a single arm BOP2 design with the interim assessment after 10 patients, a final assessment of 27 patients (half of the intended size of the combination arm) testing a null hypothesis of 15% ORR (KEYNOTE-048 pembrolizumab monotherapy ORR for this subgroup ([Burtness et al 2022](#))) vs. an alternative hypothesis of 29% ORR (SCORES combination arm for this subgroup), at 1-sided 10% level with approximately 65% power.

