9.7 Analysis of Efficacy

The primary efficacy analysis for ORR, as well as the interim analysis for PFS and OS, will be conducted once all patients are treated and followed for a minimum of 3 months (2 radiologic scans). The final analysis for PFS and OS will be conducted after all patients have been followed for a minimum of 15 months, unless the study is deemed futile at the interim or primary analysis stage.

The overall response will be assessed by the Investigator based on the RECIST v1.1 criteria at each timepoint specified the SoA ([Section 8.1](#)). The best overall response (BOR) will be assessed from response assessments occurring after the first dose of either study treatment up to the first documented assessment of PD that is prior to the initiation of a new anticancer therapy. Objective response (i.e., BOR of PR or CR) will require confirmation of the response (CR or PR) at least 4 weeks after the initial CR or PR.

The ORR will be defined as the proportion of patients with a confirmed objective response as assessed by the Investigator in the FAS. Patients who receive at least one dose of either study treatment but have no valid postbaseline radiographic assessment will be considered non-responders. The ORR will be reported along with the corresponding 2-sided 90% and 95% Clopper-Pearson exact CI. The criteria for promising ORR at the primary analysis are detailed in [Table 9](#) and, in addition, a comparison between the 2 treatment groups will be performed based on Fisher's exact test.

DOR is defined as the date of the patient's first confirmed BOR of CR or PR to the earliest date of documented progression or death if no prior evidence of disease progression, for all patients in the FAS with a confirmed objective response. A patient that starts a new anticancer therapy prior to disease progression will be censored at the date of last valid disease assessment prior to the start of the new anticancer therapy. All other patients without progression or death will be censored at the date of the last valid disease assessment. DOR will be summarized using Kaplan-Meier methods.

The DCR, which includes a BOR of CR, PR, or SD, will be analyzed similar to ORR.

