9.10.2 Futility Analysis

The BOP2 suggested futility monitoring criteria that apply for the entire study population, as well as the CPS ≥ 1 and < 20 subgroup, are presented in [Section 9.2](#) and are non-binding. At the primary analysis, a lower ORR for advancement may also suffice by taking into

Flamingo Therapeutics

Activity and Safety of Danvatirsen and Pembrolizumab in HNSCC

8 May 2025

Trial ID: FLM-6774-201

Amendment 4

consideration the CR rate that suggests superiority with regard to deep responses over that observed with pembrolizumab alone.

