10.2 Ethics Committee and Regulatory Authorities

This study will be conducted in accordance with the protocol and with the following:

- Consensus ethical principles derived from international guidelines including the Declaration of Helsinki and Council for International Organizations of Medical Sciences International Ethical Guidelines
- Applicable ICH GCP Guidelines
- Applicable laws and regulations

The Sponsor or designee will submit the study protocol plus all relevant study documents to applicable regulatory agencies for approval before the study start. No patient will be admitted to the study until appropriate regulatory approval of the study protocol has been received.

Each Investigator must complete a Form FDA 1572 or equivalent and provide the completed form according to written instructions to the Sponsor (or designee).

The study will be registered at www.clinicaltrials.gov and other trial registries as required based on the countries in which the study is conducted.

The protocol, protocol amendments, ICF, Investigator's Brochure, and other relevant documents (e.g., advertisements) must be approved by an IRB/EC before the study is initiated.

Any amendments to the protocol will require IRB/EC approval before implementation of changes made to the study design, except for changes necessary to eliminate an immediate hazard to study patients.

The Investigator will be responsible for the following:

- Providing written summaries of the status of the study to the IRB/EC annually or more frequently in accordance with the requirements, policies, and procedures established by the IRB/EC
- Notifying the IRB/EC of SAEs or other significant safety findings as required by IRB/EC procedures
- Providing oversight of the conduct of the study at the site and adherence to requirements of 21 Code of Federal Regulations (CFR), ICH guidelines, the IRB/EC,

European regulation 536/2014 for clinical studies (if applicable), and all other applicable local regulations

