### 3 SAMPLE SIZE

Sample size considerations were based on monitoring the primary efficacy endpoint, ORR, using a 2-arm Bayesian optimal phase 2 (BOP2) design.

The primary efficacy evaluation will be the magnitude of ORR in each of the treatment arms and the probability that the combination arm ORR is superior to that of the control (monotherapy) arm, that is  $\text{Pr}(\text{ORR}_{\text{comb}} > \text{ORR}_{\text{con}} | \text{data})$ .

The design is optimized to maximize the power under  $H_0$ :  $\text{ORR}_{\text{con}} = 0.15$  and  $\text{ORR}_{\text{comb}} = 0.43$ , while controlling the type I error rate at 1-sided 0.05.

An interim futility analysis is planned when ORR can be assessed for the first 39 patients, and the final ORR analysis is planned after 81 patients are followed for a minimum of 3 months (2 radiologic scans). A 2:1 combination: control randomization will be used for the 2 arms and will yield 83% power at the 1-sided 5% alpha based on the decision rule to reject the null hypothesis and conclude that the combination arm is superior compared to the control.

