## 5.12 Efficacy Analyses

All efficacy analyses will be presented by planned treatment for the FAS.

All statistical tests will be performed using a two-tailed 5% overall significance level, unless otherwise stated. All comparisons between treatments will be reported with 90% and 95% confidence intervals for the difference.

The following efficacy parameters will be derived as per RECIST v1.1 for the FAS.

- Overall Response Rate
- Disease Control Rate
- Complete Response Rate
- Duration of Response
- Progression-Free Survival
- Overall Survival

A summary of RECIST v1.1 tumor assessments, methods, and criteria are presented in Appendix 5 of the protocol. All efficacy parameters are derived from overall response as per RECIST v1.1. Overall response at each tumor assessment is determined using measurements of both target and non-target lesions. The overall response categories are as follows.

All target lesion, non-target lesion, and new lesion data will be listed separately.

Overall Response Categories by RECIST v.1.1	
CR	Complete Response
PR	Partial Response
SD	Stable Disease
PD	Progressive Disease
NE	Not Evaluable

A response of CR or PR must be confirmed by a repeat assessment at least 4 weeks after the initial CR or PR. A tumor assessment at least 35 days after the first dose is required for an overall response of SD, otherwise the BOR is considered not evaluable (NE).

Overall response rate (ORR), complete response rate (CR), and disease control rate (DCR) are each calculated using the subject's best overall response (BOR) on study. This is determined based on the following hierarchy for overall response category:

CR > PR > SD > PD > NE

Tumor assessments after the first PD will not be considered for BOR.

QMD Ref: Worldwide-TMP-ST-054-1.0_Effective: 12Aug2022	Governing QMD: Worldwide-SOP-ST-026
Confidentiality Statement	

This document is the property of Worldwide Clinical Trials Inc. and may not be duplicated, copied, altered or removed from company without prior approval from Worldwide Quality Assurance or in compliance with Worldwide Standard Operating Procedures.

Worldwide Clinical Trials Controlled Quality Management Document			
 WORLDWIDE CLINICAL TRIALS	Sponsor:	Flamingo Therapeutics	
	Protocol Number:	FLM-6774-201	
STATISTICAL ANALYSIS PLAN			

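### SAP 5.12.2 tests the primary ORR hypothesis by Fisher's exact test alone and does not link it to the posterior > 0.96 criterion that carries the 83% power

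*Protocol*

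**What the plan says.** Protocol 9.1 and SAP 3 define the primary efficacy evaluation as the size of the ORR in each arm together with the posterior probability that the combination ORR exceeds the control ORR. Protocol 9.2 gives the final criterion, "At the final analysis: $Pr(ORR_{comb} > ORR_{con} | data) > 0.96", and attributes the power to it. SAP 3 repeats that the design "will yield 83% power at the 1-sided 5% alpha based on the decision rule".

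Protocol 9.7 ranks the analyses: "The criteria for promising ORR at the primary analysis are detailed in" Table 9, with Fisher's exact test as a further comparison. Protocol 9.2 calls the criteria non-binding. Protocol 9.10.2 adds that "a lower ORR for advancement may also suffice" in light of the CR rate.

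SAP 8, headed Interim Analysis, prints the formula, the priors and the final 0.96 criterion. SAP 5.12.1 states the one-sided hypotheses. SAP 5.12.2 then specifies Clopper-Pearson intervals, a Wald risk difference and Fisher's test with both one- and two-tailed p-values, and gives code for these only. It does not mention the posterior, 0.96, Table 9 or SAP 8. The general rule in SAP 5.12 is: "All statistical tests will be performed using a two-tailed 5% overall significance level, unless otherwise stated". SAP 9 says the final analysis will come early because the study was terminated.

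For the interim, Protocol 9.2 and SAP 8 print a cut-off formula and also the wording "At the interim analysis: $Pr(ORR_{comb} > ORR_{con} | data) > 0.5".

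**The concern.** A statistician who follows the SAP's primary-analysis section would judge the primary hypothesis by Fisher's test. The protocol's criterion and the quoted power belong to a different, less conservative rule. The same data could then be called promising under Protocol 9.7 and not significant under SAP 5.12.2, with nothing in the SAP to say which reading governs. SAP 5.12.2 does not say which p-value decides either, and the two-tailed default does not match a one-sided 5% design.

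Early termination sharpens this. The final rows of Table 9 hold only for 27 control and 54 combination patients, so the posterior must be computed directly, and SAP 5.12.2 does not say how. SAP 8 also carries a cut-off that scales with n/N, which could be applied by mistake at a reduced final N.

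The interim wording is a smaller matter: > 0.5 is not the value that the formula gives.

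**Working it through.** ORR pairs below are control/combination.

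**Inputs** (Protocol 9.2): λ = 0.96, exponent 0.94, Beta(0.5, 0.5) priors; interim 13 control and 26 combination patients; final 27 and 54; design point 15/43; type I error at 15/15.

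**Method.** With x responders of n, each arm's posterior is Beta(x + 0.5, n − x + 0.5). Pr(ORR_comb > ORR_con | data) is the integral of the control density times the upper tail of the combination distribution. Every outcome was enumerated exactly. Interim outcomes that continue were combined with the further 14 control and 28 combination patients.

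**1. The plan's own figures.** The interim cut-off is 0.96 × (39/81)^0.94 = 0.483. With 0.483 and 0.96, all 14 interim and all 28 final rows of Table 9 reproduce. Claim rates are 82.6% at 15/43 (Table 10: 82.7%), 54.4% at 20/40 (54.6%) and 4.5% at 15/15 (4.6%). The 83% therefore belongs to the posterior rule.

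**2. The same design judged by Fisher at N = 81** (interim cut-off 0.483; two-tailed p ≤ 0.05 counted only when it favours the combination):

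| Final rule | Power 15/43 | Power 20/40 | Type I error 15/15 |
|---|---|---|---|
| Posterior > 0.96 | 82.6% | 54.4% | 4.5% |
| Fisher one-tailed ≤ 0.05 | 77.8% | 47.7% | 2.1% |
| Fisher two-tailed ≤ 0.05 | 71.0% | 39.4% | 1.2% |

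Across all 55 × 28 final outcomes, Fisher never succeeds where the posterior fails. The conflict rate at 15/43 is therefore the difference in power: 82.6 − 77.8 = 4.8% of trials (one-tailed) or 82.6 − 71.0 = 11.6% (two-tailed).

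**3. Example.** With 4/27 control and 18/54 combination responders, the posteriors are Beta(4.5, 23.5) and Beta(18.5, 36.5). The probability is 0.965, which passes. Fisher gives p = 0.064 (one-tailed) and 0.112 (two-tailed). The smallest successful combination count against 4/27 is 18 for the posterior, 19 for one-tailed Fisher and 20 for two-tailed Fisher.

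**4. Early final analysis.** The documents do not give the actual N. The table assumes 2:1 allocation and a single look. The last two columns show what happens if the actual n were put into the SAP 8 formula, 0.96 × (n/81)^0.94.

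| N | Power 15/43, 0.96 rule | Power 15/43, one-tailed Fisher | Type I 15/15, 0.96 rule | Type I 23/23, 0.96 rule | Rescaled cut-off | Type I 15/15, rescaled |
|---|---|---|---|---|---|---|
| 39 | 52.7% | 43.1% | 4.5% | 4.3% | – | – |
| 51 | 64.5% | 55.9% | 4.9% | 4.5% | 0.621 | 35.0% |
| 60 | 72.7% | 62.6% | 5.0% | 4.7% | 0.724 | 28.6% |
| 69 | 77.6% | 71.6% | 5.1% | 4.8% | 0.826 | 18.5% |

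**5. Interim wording.** The cut-offs 0.483 and 0.5 differ for five outcomes only: 2, 3, 4, 5 or 6 control responders with exactly twice as many combination responders (posterior 0.484 to 0.499). Table 9 continues there; > 0.5 stops. At 0 and 0, and at 1 and 2, both stop (0.393, 0.473). From 7 and 14 upward both continue (0.501 or more). Compared with the "Early Futility Stopping" column of Table 10:

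| ORR | 0.483 | 0.5 | Table 10 |
|---|---|---|---|
| 15/15 | 46.4% | 54.8% | 46.1% |
| 23/23 | 44.1% | 54.3% | 43.8% |
| 20/40 | 7.1% | 11.1% | 7.1% |
| 23/43 | 7.8% | 11.8% | 7.7% |
| 25/50 | 4.5% | 6.9% | 4.5% |
| 15/43 | 1.9% | 3.4% | 1.9% |

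Table 10 follows 0.483. Power at 15/43 is 82.6% against 82.2%, and type I error at 15/15 is 4.5% under both.

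**The case against.** The best defence is that the rule is already in the SAP. SAP 3 names the posterior probability, SAP 8 prints the prior and the 0.96 criterion for rejecting the same null, and Protocol 9.7 supplies the ranking, so SAP 5.12.2 merely specifies the additional test. That is true, and it limits the defect to a missing link and ranking. It does not remove it: SAP 5.12.2 specifies the primary analysis and does not point to SAP 8.

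The criteria are also non-binding. This governs how the result is used, not which analysis is primary, but it does lower the stakes.

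The 71.0% is the least favourable reading, since SAP 3 and 5.12.1 are one-sided; the one-tailed comparison, about 5 points, is the fairer one. No title in the SAP 11 list names the posterior probability, but the TFL shells were not available, so this is weak evidence. Rescaling 0.96 by n/N would be a misreading, because Protocol 9.2 defines n as the interim size; one sentence would rule it out. Finally, neither document sets a rule for an unplanned final N. Holding 0.96 is a proposal, and at an assumed N of 69 its type I error is 5.1%, marginally above the 5% design level.

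On the interim, 0.5 may be a rounding of 0.483, and Table 9 already gives the exact boundaries.

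**Conclusion.** The concern holds and should be fixed, as an alignment matter. The protocol's primary criterion is the posterior rule; the SAP's primary-analysis section implements only Fisher's test and does not connect the two. If Fisher decided, power at 15/43 and N = 81 would fall by 4.8 points (one-tailed) or 11.6 points (two-tailed default). Error control would not be lost, because every disagreement has the posterior passing and Fisher failing.

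The N = 81 figures rest on the documents' priors, response rates and allocation. The early-analysis figures rest on assumed sample sizes and a single look. Under those assumptions, the 83% does not describe the analysis that will actually be run, whichever test is used.

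The interim discrepancy is real but minor. It changes power by 0.4 points (82.6 − 82.2) and may have no further use, since the documents do not say whether the interim took place.

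**What to change.** Add to SAP 5.12.2, in substance:

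> The primary ORR criterion is Pr(ORR_comb > ORR_con | data) > 0.96 with Beta(0.5, 0.5) priors, computed at the actual number of patients per arm; 0.96 is not rescaled by n/N. It is non-binding and subject to Protocol 9.10.2. Fisher's exact test is supportive.

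- Compute the probability directly rather than reading it from Table 9, and add it to Table 14.2.1.1.
- State in SAP 5.12 that the two-tailed 5% default does not govern this criterion.
- Note in SAP 3 that the 83% applies to the posterior rule at N = 81.
- In SAP 9, say how the rule applies at the early analysis, and report its power and type I error at the actual N.
- Minor: in SAP 8, replace > 0.5 with ≥ 0.483 (Protocol Table 9), and record the difference from Protocol 9.2's wording in SAP 9.

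The cost is one or two sentences in each of SAP 3, 5.12, 5.12.2 and 9, one number in SAP 8, and one output value. SAP 5 requires approval before database lock and an addendum afterwards; the documents do not give the lock status. Correcting Protocol 9.2 would need an amendment (Protocol 10.2: "Any amendments to the protocol will require IRB/EC approval before implementation of changes made to the study design"), which the interim wording does not justify on its own. Correct it there only if the protocol is amended for another reason.

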9.3 Analysis Populations

9.3.1 Full Analysis Set

The Full Analysis Set (FAS) will include all patients who receive at least 1 dose of study treatment based on the treatment assigned at randomization and will be the primary analysis set for efficacy analyses.

9.3.2 Safety Analysis Set

The Safety Analysis Set (SAS) will include all patients who receive at least 1 dose of study treatment based on the actual treatment received and will be the primary analysis set for safety analyses.

9.3.3 PK Evaluable Set

The PK Evaluable Set will include all FAS patients with evaluable PK data.

9.3.4 Biomarker Evaluable Set

The Biomarker Evaluable Set will include all FAS patients with evaluable biomarker data.

9.4 General Considerations

Descriptive statistics will be used to display the results. Continuous variables, including baseline characteristics, will be summarized by reporting the number of observations, mean, standard deviation, median, minimum, and maximum. Categorical/discrete variables will be summarized using frequency tables showing the number and percentage of patients within a category.

For time-to-event endpoints, the median, 25th and 75th percentiles (if estimable) using Kaplan-Meier methods along with the 90% and 95% confidence intervals (CIs) will be reported. Kaplan-Meier curves will also be generated for each time-to-event endpoint.

Missing data will not be imputed except as described in the SAP. Baseline value will be defined as the last non-missing value before receipt of the first dose of study treatment.

9.5 Disposition, Demographic and Baseline Characteristics, and Exposure

The number of patients in each study population and the reasons for exclusion will be summarized.

Patient demographics, baseline characteristics, and exposure will be listed and summarized for the FAS. Patient attributes will be summarized using frequency distributions for categorical variables or descriptive statistics for continuous endpoints, as appropriate.

Descriptive information for danvatirsen and pembrolizumab will be provided regarding the number of doses administered, the number of dose modifications and delays, the duration of treatment, and the relative dose intensity (% of treatment administered compared to targeted).

